- a. Does your YNHH privilege delineation currently include the **specific procedure** that you will perform? Yes No
- b. Will you be using any new equipment or equipment that you have not used in the past for this procedure? Yes No
- c. Will a novel approach using existing equipment be applied? Yes No

If you answered "no" to question 4a, or "yes" to question 4b or c, please contact the YNHH Department of Physician Services ([name]) for prior approval before commencing with your research protocol.

IMPORTANT REMINDER ABOUT RESEARCH AT YNHH

Please note that if this protocol includes Yale-New Haven Hospital patients, including patients at the HRU, the Principal Investigator and any co-investigators who are physicians or mid-level practitioners (includes PAs, APRNs, psychologists and speech pathologists) who may have direct patient contact with patients on YNHH premises must have medical staff appointment and appropriate clinical privileges at YNHH. If you are uncertain whether the study personnel meet the criteria, please telephone the Physician Services Department at [contact]. **By submitting this protocol as a PI, you attest that you and any co-investigator who may have patient contact has a medical staff appointment and appropriate clinical privileges at YNHH.**

SECTION I: RESEARCH PLAN

1. **Statement of Purpose:** State the scientific aim(s) of the study, or the hypotheses to be tested.

We propose to examine, in 172 women newly diagnosed with Stage I-III breast cancer who are not practicing the dietary and lifestyle guidelines, and who will receive neoadjuvant or adjuvant chemotherapy as part of their treatment, the effect of a 1-year dietary and physical activity guidelines intervention vs. usual care on the breast cancer outcomes described below. Women will be enrolled either before beginning chemotherapy or following the first chemotherapy infusion but prior to the second chemotherapy infusion (Time 0). Follow up visits will occur post chemotherapy (Time 1), at one-year post-diagnosis (Time 2), at two years post-diagnosis (Time 3) and at five years post-diagnosis.

Primary Endpoints: Adherence to Breast Cancer Treatments

Aim 1a: Chemotherapy completion rates (dose amount, number of dose reductions and dose delays)

Aim 1b: Adherence to endocrine therapy in women taking tamoxifen or Aromatase Inhibitors (AIs) at 12- and 24-months after enrollment

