Relative dose intensity will be calculated using the methods described by Longo et al [24]. The primary endpoint, RDI will be analyzed both as a continuous scale using the t test, and as a dichotomized outcome using 85% or 95% cut-off for Mantel-Haensel chi-square test controlling for stratification factors. In addition, group differences in chemotherapy completion rates will be analyzed with binary logistic regression analysis; whether or not having dose reduction during the period of chemotherapy treatment (the period between T0 and T1) will be the dichotomized dependent variable. The outcome of endocrine therapy adherence will be assessed at the 2 and 5-year follow ups (as most, if not all, participants prescribed endocrine therapy will have been taking it for at least 1 year at the 2-year visit, allowing us to assess adherence to endocrine therapy). The primary endocrine therapy outcome will be adherence to endocrine therapy assessed via the electronic medical records. Note: the assessment for the primary outcome of endocrine therapy adherence was changed from the initial assessment (urinary metabolites) as the COVID pandemic limited our ability to collect urine samples.

Secondary assessments of endocrine therapy will be:

a) Urinary AI level. An undetectable level will classify the participant as nonadherent to AIs.

b) Responses to the following questions:

(1) “In the past month, how often did you take your medications as the doctor prescribed?” Possible responses are all of the time (100%), nearly all of the time (90%), most of the time (75%), about half the time (50%), or less than half the time (<50%). Nonadherence is defined as 75% of the time or less.

(2) “In the past month, how often did you forget to take 1 or more of your prescribed medications?”

Possible responses were never, once in the past month, 2 to 3 times in the past month, once per week, several times per week, and nearly every day. Nonadherence is defined as forgetting to take prescribed medications once per week or more.

(3) “In the past month, how often did you decide to skip 1 or more of your prescribed medications?”

Possible responses were the same as for question 2. Nonadherence is defined as deciding to skip medications once per week or more. The first will be the primary measure of non-adherence. (73,74).

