Participants who report that they have discontinued taking tamoxifen or AI will also be classified as nonadherent to endocrine therapy. For patients who may be lost to follow-up, we will obtain prescription refill data as an endpoint of adherence to endocrine therapy. For the endocrine

therapy aim, we will compare the crude adherence rates using simple logistic regression. Multivariate logistic regression will serve as supportive analyses including covariate adjustments – which are similar to the primary analysis above.

The secondary aims will be performed using Mixed Model Repeated Measures analysis incorporating Analysis of Covariance, where each woman's changes in outcome (follow-up measure – baseline) will be modeled as a function of treatment and time with a covariate included for the baseline value. Prior to fitting models, we will perform exploratory data analyses focusing on the distributions of biological markers by time and intervention group, assessing the appropriateness of log-transformation.

All hypotheses will be tested according to the intention-to-treat philosophy in which all randomized participants will be grouped according to their intervention assignment at randomization, regardless of compliance or adherence to the study. Statistical significance will be defined as $p < 0.05$, 2-sided. Since we have multiple outcomes, we will consider using a Bonferroni correction.

Age, menopausal status, race/ethnicity, BMI at diagnosis, disease stage, type of surgery, type of chemotherapy, radiation therapy, hormone receptor status, endocrine therapy, reconstructive surgery, type 2 diabetes, and smoking status will be examined as covariates. We will explore effect modification by menopausal status at diagnosis, hormone receptor status, and endocrine therapy.

We will further explore intervention effects on study endpoints by stratifying by adherence to diet and physical activity guidelines with a four-level category (e.g., met diet recommendations, met physical activity, met both diet and physical activity recommendations, or met neither recommendation). This analysis will allow us to better understand the role of diet vs. exercise on study endpoints.

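### The covariate list and the endocrine-therapy effect modifier are not limited to values known at randomization, so supportive and exploratory adjusted arm effects may be biased

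*Combined protocol and SAP*

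**What the plan says.** All references are to the combined protocol and SAP, Section I.

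- **Covariates (item 12).** One sentence names the candidate covariates. Besides age, stage and similar factors it includes type of surgery, and it ends: "radiation therapy, hormone receptor status, endocrine therapy, reconstructive surgery, type 2 diabetes, and smoking status will be examined as covariates". BMI is tied to diagnosis. The treatment variables carry no time point, and the text does not say whether they are coded as planned or as received.
- **Effect modification (item 12).** "We will explore effect modification by menopausal status at diagnosis, hormone receptor status, and endocrine therapy". Menopausal status is dated; endocrine therapy is not.
- **Main analyses (item 12).** "RDI will be analyzed both as a continuous scale using the t test"; dichotomized RDI uses a "Mantel-Haensel chi-square test controlling for stratification factors". For endocrine adherence, "we will compare the crude adherence rates using simple logistic regression". The secondary-aim repeated-measures model names treatment, time and the baseline value.
- **Adjusted adherence model (item 12).** "Multivariate logistic regression will serve as supportive analyses including covariate adjustments". The sentence then says that these adjustments resemble those of the primary analysis described before it.

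**The concern.** Women are randomized before their second chemotherapy infusion. A variable settled after that point can be changed by the arm, by how chemotherapy was tolerated, or by how the tumour responded. Conditioning on such a variable can remove part of a real arm effect or create one where there is none. A subgroup formed by later treatment is likewise not a comparison that randomization protects.

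The trial's own hypotheses make the link to arm plausible. Aim 1b proposes that the intervention changes endocrine adherence. Aim 5 compares tumour response by arm, and the Background (Lifestyle Interventions and Pathologic Outcomes) connects neoadjuvant shrinkage with more breast-conserving surgery.

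At stake is how the supportive results are read. If crude and adjusted estimates disagree, a reader could not tell control of chance imbalance from over-adjustment.

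**Working it through.** **1. When each variable is settled**

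- *Time 0:* before chemotherapy, or after the first and before the second infusion (item 1).
- *RDI and dose-reduction window:* Time 0 to Time 1, the end of chemotherapy (items 1 and 12).
- *Surgery:* before baseline in adjuvant women, after it in neoadjuvant women (item 3a). In the latter it also follows the RDI window.
- *Endocrine therapy:* item 12 expects at least one year of use at the 2-year visit. The assessment table (item 3c) schedules the tamoxifen/AI usage form from year 1 on, not at baseline or post-chemotherapy. Both place it after Time 0, and the schedule places it after chemotherapy.
- *Radiation and reconstruction:* no timing is given. In adjuvant women reconstruction may precede baseline.
- *Coding:* item 3c (medical history) has surgery, and endocrine therapy with its start date, abstracted from the medical record to confirm treatment. This points to treatment as received but does not settle it.

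**2. The plan's own figure**

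Inputs (item 12, Power): difference 0.05, SD 0.10, two-sided 0.05, power 90%.

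n = 2(1.960 + 1.282)²(0.10/0.05)² = 84.1, so 85 per arm by the normal approximation. By the noncentral t, 85 per arm gives 89.99% and 86 gives 90.3%. The stated 86 reproduces. It rests on an unadjusted comparison, so the covariate list does not enter it.

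**3. If the list were applied to RDI**

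Let Y = bT + e be RDI and M = cY + d a covariate that follows it, with within-arm correlation r. The slope of Y on M within arm is r²/c, and M differs between arms by cb. The arm coefficient given M is therefore b − (r²/c)(cb) = b(1 − r²). With b = 5 points and r assumed:

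- r = 0.2: 5 × 0.96 = 4.8, a loss of 0.2 (4%)
- r = 0.4: 5 × 0.84 = 4.2, a loss of 0.8 (16%)

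A simulation with a binary covariate (1,000,000 records, linear model, true difference 0.05, SD 0.10) gave 0.0504 unadjusted. The adjusted results, by assumed odds ratio of the covariate per SD of RDI, were:

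- 1.00: 0.0504
- 1.28: 0.0497
- 1.65: 0.0477
- 2.72: 0.0421
- 4.48: 0.0366

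When the covariate depended on arm only, the estimate stayed at 0.0504.

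**4. No true effect, with a shared cause**

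Here a prognostic factor U contributes 0.06 per SD to an outcome with SD √(0.06² + 0.08²) = 0.10. The covariate depends on arm (log-odds d) and on U (log-odds g per SD). The false arm effects were:

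- d = 0.5, g = 0.5: −0.0033, or −0.03 SD
- d = 0.5, g = 1: −0.0051, or −0.05 SD
- d = 1, g = 1: −0.0086, or −0.09 SD
- either link set to zero: between 0.0000 and 0.0001 in absolute value

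For scale, the planned insulin effect is 3.0/8.0 = 0.375 SD (item 12).

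**5. The endocrine-therapy subgroup**

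The plan expects about 70% to be prescribed endocrine therapy: 0.70 × 86 ≈ 60 per arm. If the modifier means prescribed, and prescription follows receptor status, the subgroup is about 60 against 60. If it means adherent use, the plan's hypothesis of 75% against 50% makes it about 45 against 30, so the arm itself selects the subgroup. The text does not say which is meant.

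**The case against.** The other side is strong on several points, and these stand:

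- No written main model contains the disputed variables. The RDI, adherence and secondary analyses are unadjusted, stratified on factors set before randomization, or adjusted only for the baseline value. The dose-reduction logistic model names no covariates.
- The list says the variables are to be examined, not included.
- The phrase likening the adherence adjustments to the primary analysis may mean only the stratification factors, since the Mantel-Haenszel test is the one adjustment described before it.
- Prescription of endocrine therapy probably tracks hormone receptor status, a stratification factor: the Background puts about 70% of breast cancers as receptor-positive, and the plan expects about 70% to be prescribed it.
- Every link strength used for size is assumed.

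What does not stand is that nothing needs changing. This is the only general covariate list in item 12 and it names no endpoint, so nothing keeps it out of the adjusted models. Leaving inclusion open defers the choice until data are in hand. Receptor status largely governs who is offered endocrine therapy, but not who starts or continues it.

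A reader might infer that an RDI model adjusted for later treatments is already specified, or that every adjusted arm effect fails as an effect of assignment. The documents support neither. No such RDI model is written out, and bias needs a link to the outcome, not merely a variable recorded later.

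**Conclusion.** The gap is real but confined to supportive and exploratory analyses. The covariate list and the endocrine-therapy modifier admit variables that the plan's own timeline puts after randomization: endocrine therapy, and surgery in neoadjuvant women. Radiation and reconstruction are possible further cases that the documents do not date. Used as received, these variables can bias an adjusted arm effect; if the list were applied to RDI, the two datable ones also follow the outcome.

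Under the assumed links, the loss for RDI is 0.2 to 0.8 of 5 points by the closed form. In simulation the adjusted difference ranged from essentially unchanged down to 0.037. A false effect of 0.03 to 0.09 SD arises where there is no true one. All of these go to zero if the covariate has no link to the outcome.

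The main tests, the intention-to-treat grouping, the 172 and the stated power are untouched.

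**What to change.** In item 12:

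- Limit covariates in adjusted arm comparisons to values fixed at Time 0: age, race/ethnicity, menopausal status, BMI and stage as at diagnosis, planned chemotherapy regimen, receptor status, diabetes and smoking. Allow surgery or reconstruction only where it preceded randomization.
- Remove radiation and endocrine therapy as received.
- State which models use the list, and say what the adherence model's adjustments are meant to resemble.
- Use the hormone-receptor-status modifier already named in place of endocrine therapy, or keep the endocrine-therapy subgroup and label it exploratory and non-causal. The planned analysis "stratifying by adherence to diet and physical activity guidelines with a four-level category" is also formed after randomization and should carry the same label.

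The cost is wording only: no new data, and no change to sample size, power or the main analyses.

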Women will be asked to complete the self-administered study questionnaires prior to the in-person baseline visit. They will be provided a link via email to the online questionnaires or given a hard copy version if preferred.

Assessments	Screening	Baseline	Post-chemo	1-year	2-year	5-year
Screening Questionnaire	X					
Demographic Questionnaire*		X				
Medical History Questionnaire*		X				
Food Frequency Questionnaire		X	X	X	X	X

Phone assessment 24-hour dietary recall – 1-day ^{&1}		X	X	X	X	
Physical Activity Questionnaire		X	X	X	X	X
Patient Global Assessment (SGPGA)	X					
PROMIS quality of life questionnaires(74)		X	X	X	X	X
Prescription Medication		X	X	X	X	X
Adherence to medication questionnaire(75, 76)				X	X	X
Neuropathy – EORTLC QLQ-CIPN20(77)		X	X	X	X	X
Work history			X	X	X	X
Beliefs about Medication Questionnaire(78)				X	X	X
Treatment Satisfaction Questionnaire for Medication(79)				X	X	X
Health Insurance, prescription coverage and prescription refill habits				X	X	X
Medication usage questionnaire				X	X	X
Aromatase Inhibitor/Tamoxifen usage form				X	X	X
Breast Cancer Prevention Trial (BCPT) Symptom Scales (80)		X	X	X	X	X
Brief Pain Index		X	X	X	X	X
Homunculus		X	X	X	X	X
Y5-Lymphedema Questionnaire						X
Supplement intake/over the counter medication *		X	X	X	X	X
Y1 -Lymphedema Questionnaire				X		
Y2- Lymphedema Questionnaire					X	
Satisfaction Questionnaire (Intervention group)				X		
Side-effects and toxicity assessment (PRO-CTCAE™)		X	X			
Chemotherapy delay/dose reduction/reasons (extracted from EPIC EMR)			X			
Grip Strength [%]		X	X	X	X	
EPIC 2YR follow up treatment form					X	

EPIC 5 Year medical usage and breast cancer status abstraction						X
Two Year Follow up Treatment form'					X	
Height and weight measured [%]		X	X	X	X	
Waist and hip circumference measured [%]		X	X	X	X	
Blood collection [%]		X	X	X	X	
DXA scan [%]		X	X	X	X	
Urine collection ^{%@}				X	X	
Urine collection for pregnancy test if applicable prior to DEXA [%]		X	X	X	X	
Stool collection [%]		X	X	X		
Skin carotenoids [%]		X	X	X	X	

*: Part of the Baseline Questionnaire

%: Applicable only to the Yale site when in-person visits are completed. Assessments are optional.

@ Applicable to women who are prescribed an aromatase inhibitor

&: Assessment is optional.

1: Discontinued in August 2020.

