Medical history and demographic questionnaires: The following will be assessed via questionnaire prior to enrollment and at 1- 2- and 5-years (when applicable): reproductive and menstrual history, medical history, family history of breast and other specific cancers, and history of tobacco and alcohol. Menopausal status will be defined at diagnosis as 12 months of amenorrhea; perimenopause will be defined as amenorrhea for 3 months in the previous 12 months. Self-report of menses is viewed as reliable to define menopausal status, especially since serum hormonal levels are highly unreliable in the perimenopausal transition phase. To confirm therapy and other treatments, the following will be abstracted from medical records via EPIC: surgery, presence or number of involved axillary lymph nodes, hormone receptor status, disease stage, tumor size, chemotherapy therapy and evidence of completion (see also our section on chemotherapy completion rate); type of endocrine therapy (if applicable) including start date (see section on Adherence to Endocrine Therapy). All current prescription and over-the-counter medications will also be inventoried.

Physical Activity: Women will complete a physical activity questionnaire to assess current (past week) and past year (i.e., year before diagnosis) physical activity levels. Hours/week spent in different types and intensities of activity (including sedentary time) will be computed over the past week and year before diagnosis, as well as at 1-year 2-year and 5-year follow ups.. This physical activity questionnaire has been used in all of [name] previous studies and has been extensively published and shown to be valid and reliable.(19) Women randomized to intervention will be given Fitbit devices which will be used as an objective measurement of physical activity. Participants will wear the Fitbits and they will be encouraged to wear the Fitbit at all times and record the steps per day in their LEANer log.

Dietary Intake: Women will complete a 120-item food frequency questionnaire (FFQ) which was developed for the Women's Health Initiative Study and has been validated against 4-Day Food Records and 24-hour Dietary Recalls (discontinued August 2020).(84) FFQs will be administered at baseline, post-chemotherapy, 1- and 2-years. The FFQ will be completed at the 5-year follow up. Subjects will have the option of completing an online version of the questionnaire. A link will be sent to the subject

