to allow completion. No PHI will be collected by the Fred Hutchinson Cancer Research Center who oversee collection of the FFQ data. No IP addresses are accessed/collected.

Adherence will be assessed via attendance to counseling sessions, as well as by adherence to the diet and physical activity recommendations (assessed via questionnaire at baseline, 1, and 2 years). Women randomized to intervention will also complete a daily log book where they log their daily food, beverages and physical activity (similar to our LEAN and HOPE studies). At each counseling session, the dietitian will review the log book either in person or via phone reporting.

*Weight and Height: Weight and height will be measured by research staff at baseline, post chemotherapy, 1- and 2-years. Participants will be weighed in light clothing, without shoes, rounding up to the nearest 0.1 kg; height will be measured in a standard manner, without shoes, using a stadiometer, rounding up to the nearest 0.1 cm. (Yale in-person visit only)

*Waist and Hip circumference: Waist and hip circumference will be measured at baseline, post-chemotherapy, 1- and 2- years. Each measurement will be taken twice by a research member. (Yale in-person visit only)

*Grip strength will be measured by a simple to administer modified sphygmomanometer (Detecto DHS Series, Northbrook, Illinois). The participant will be asked to squeeze the balloon of the sphygmomanometer three times with maximal force. The average value of three trials for each hand will be recorded. Higher scores (reported in kPa) reflect better grip strength. (Yale in-person visit only)

Pain: Pain will be assessed using the Brief Pain Index (85). Arthralgia will be assessed using a self-assessment tool where patients are asked to mark 'yes' were asked to mark painful joints on a homunculus with circles showing upper and lower extremity joints, and four areas of the back and neck, and additional diagrams of both hands (three joints on each finger and thumb) and both feet (joints at the base of each toe). (76).

Body Image: Body image will be assessed using the PROMIS assessment.

Supplement intake/over the counter medication: These will be assessed using a questionnaire used in prior studies overseen by [name].

Prescription medication: Patients will be asked to self-report current prescription medication usage.

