Usual Care Group: Both our usual care group and intervention group will be provided with standardized breast cancer follow up care and materials regarding treatment (i.e., chemotherapy and endocrine therapy when relevant). Current chemotherapy regimens vary from 3 months to 5 months. About one-third of patients will receive four cycles of chemotherapy every 3 weeks, a total duration of ~3 months. About two-thirds of patients will receive four cycles of chemotherapy every 2 weeks followed by 12 weekly cycles of chemotherapy, a total duration of ~ 5 months. Each patient sees her medical oncologist at each chemotherapy session, and also at one- and two-months post-chemotherapy, and then every 3-6 months thereafter up to two years. Patients are seen semi-annually or annually; those on endocrine therapy are monitored by their oncologist semi-annually. Holiday cards will be mailed to all women while in study.

Lastly, we will also give women randomized to usual care a lifestyle intervention book and log book for breast cancer survivors and access to the associated online videos (approved for HIC protocol 1410014716).. Women will also be offered a counseling session with a registered study dietician at the end of the study.

Dietary and Physical Activity Guidelines Intervention Group:

When and Where: Patients receiving chemotherapy see their medical oncologist at least monthly during chemotherapy and then monthly or bi-monthly, ultimately tapering to semi-annually for several years. Thus, we have designed our intervention to be implemented in the breast clinic when the patient is seeing her medical oncologist. All intervention sessions can be completed by phone or video if this is the preference of the subject. Our LEAN study compared in-person lifestyle counseling to telephone-counseling, and found similar effectiveness on changes in diet and physical activity. For the proposed study, we have adapted our LEAN intervention to include a total of 16 x 30-min sessions over 12 months (3 times in the first month, then 2 times each month for months 2 through 5, and then 5 times over the next 6 months) timed with their oncology visit or via telephone or video (doxy.me) if preferred.

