Goals of the Intervention: The goal of the intervention is for participants to adopt and practice the recommended dietary and physical activity guidelines. We will measure adherence to the dietary guidelines by whether participants meet the Healthy Eating Index 2010 (HEI-2010), as it aligns with the DHHS 2010 dietary guidelines, and has been found to be a valid and reliable measure of diet quality. We will update with HEI-2015 when available and we will also evaluate changes in intake of food group, total energy and energy from fat.

Procedures to Enhance Adoption of the Lifestyle Guidelines: Adherence will be assessed via attendance to counseling sessions, as well as by adherence to the diet and physical activity recommendations (assessed via questionnaire at baseline, 1, and 2 years). Women randomized to intervention will also complete a daily log book where they log their daily food, beverages and physical activity. At each counseling session, the dietitian will review the log book. Women randomized to intervention will also be given a Fitbit. The account will be accessible by both the subject and the research team to allow data to be accessed by the research team members. We have also developed an intervention book (adapted from the LEAN book). The books provided to the intervention group include information on skills to support behavior change. Consistent with social cognitive theory, (92) the information will emphasize increasing self-regulatory skills and using cognitive behavioral techniques such as cognitive restructuring, modeling, monitoring behavior, seeking social support, and self-reward. In summary, we designed the intervention based on our trials and to be scalable and implemented in the breast clinic.

To help those women in the intervention group comply with the intervention goals during and following the COVID-19 pandemic, all women who have been assigned to the intervention group will be emailed

- i) the link to the YouTube video in which [name] discusses the conduct of the LEANer study during the pandemic and how to adapt exercise regimens during COVID-19 restrictions. <https://www.youtube.com/watch?v=p7mA6tBlQz8>.
- ii) the link to video on safe grocery shopping practices during pandemic <https://youtu.be/3TtHg5XgZzI>

The videos will also be provided on the LEANer website tab accessible only by the intervention group participants.

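### Stratifying intervention effects by post-randomization guideline adherence cannot separate diet from exercise, and for RDI and dose adjustment every scheduled follow-up questionnaire comes after the outcome is complete

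*Combined protocol and SAP*

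**What the plan says.** Section I, item 12 (Statistical Considerations), after the intention-to-treat statement and the covariate list, adds: "We will further explore intervention effects on study endpoints by stratifying by adherence to diet and physical activity guidelines with a four-level category". The example levels are diet met, activity met, both met and neither met. The purpose follows: "This analysis will allow us to better understand the role of diet vs. exercise on study endpoints". The text names no visit, does not limit the endpoints, and does not say how usual-care women are classified.

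Guideline adherence is timed in the Study Assessments text and again under Procedures to Enhance Adoption of the Lifestyle Guidelines. Besides counselling attendance, both refer to "adherence to the diet and physical activity recommendations (assessed via questionnaire at baseline, 1, and 2 years". The schedule of assessments adds a post-chemotherapy measurement: the row "Physical Activity Questionnaire" is marked at baseline, post-chemo, 1, 2 and 5 years, and the diet text says "FFQs will be administered at baseline, post-chemotherapy, 1- and 2-years". For activity the recall is short: "Women will complete a physical activity questionnaire to assess current (past week) and past year (i.e., year before diagnosis) physical activity levels".

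The Usual Care Group section says "Current chemotherapy regimens vary from 3 months to 5 months", and item 12 places dose reductions between T0 and T1.

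**The concern.** Two separate problems arise.

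**No randomized contrast.** Women are randomized to a combined diet and activity programme or to usual care. Whether a woman then meets the diet guideline, the activity guideline, both or neither is decided after randomization, by her own circumstances and partly by the intervention. Usual-care women who meet both guidelines do so unaided, whereas many intervention women do so with coaching. Comparing arms within that stratum compares differently selected women. Comparing strata within an arm compares self-selected groups. Neither comparison isolates diet from exercise, for any endpoint.

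**Order in time, for RDI and dose adjustment.** RDI is complete when chemotherapy ends. A woman whose toxicity led to reductions or delays may also be less able to eat well or exercise afterwards. Adherence recorded after the last infusion can then be a result of the outcome rather than a cause of it.

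At stake is a published statement about which component matters. Women who tolerated chemotherapy well could make adherence look protective, and an ineffective intervention could look harmful within strata.

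**Working it through.** **1. The plan's own figure.** Item 12 gives 86 per arm for 90% power, difference 0.05, SD 0.10, two-sided 0.05. The normal approximation is n = 2 x (1.960 + 1.282)^2 x 0.10^2 / 0.05^2 = 84.1, so 85; the noncentral t gives 86 (power 90.3%). The figure reproduces and is not disputed. It fixes the scale: SD 10 points, target 5 points.

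**2. Timing, side by side.**

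| Item | When | Source |
|---|---|---|
| RDI, dose adjustment | T0 to T1; regimens of 3 to 5 months | Item 12; Usual Care Group |
| Food frequency and activity questionnaires | Post-chemo, 1 and 2 years | Schedule of assessments |
| Guideline adherence by questionnaire | Baseline, 1 and 2 years | Study Assessments; Procedures to Enhance Adoption |
| Counselling attendance, log book, Fitbit | During chemotherapy, intervention arm only | Study Assessments; Procedures to Enhance Adoption |

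Every follow-up questionnaire available in both arms comes after RDI is complete. The only records made during chemotherapy are in the intervention arm, so they cannot stratify an arm comparison.

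**3. Illustration of the bias.** From the documents: SD 0.10. Assumed: no intervention effect; each guideline met by 20% in usual care and 50% in the intervention arm; one tolerance factor loading equally (r) on RDI and on the tendency to meet each guideline, so every pairwise correlation is rho = r^2. With r = 0.30, 0.40 and 0.55, rho = 0.09, 0.16 and 0.3025.

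The mean standardized RDI among women meeting both guidelines is

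m = 2 rho phi(c) Phi(-c sqrt((1 - rho)/(1 + rho))) / P(both),

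where c is the normal cut-off for the adherence rate. In the intervention arm c = 0, so m = 0.3989 rho / P(both), with P(both) = 1/4 + arcsin(rho)/(2 pi). Met-neither is the mirror image, so the difference is 2 x 10 x m points. For rho = 0.09: m = 0.0359 / 0.2643 = 0.136, giving 2.7 points. In usual care c = 0.842 and m = 0.235, so the arm difference within met-both is 10 x (0.136 - 0.235) = -1.0 point.

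| rho | Both minus neither, intervention arm | Intervention minus usual care, met-both | Intervention minus usual care, met-neither |
|---|---|---|---|
| 0.09 | +2.7 | -1.0 | -0.8 |
| 0.16 | +4.6 | -1.7 | -1.3 |
| 0.30 | +8.1 | -2.8 | -2.2 |

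The truth in every cell is 0. Simulation agrees within about 0.1 point. Diet-only minus exercise-only is about 0 throughout, because the loadings were set equal; unequal loadings would change that.

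**4. Sensitivity.** Normal RDI with mean 0.90 (assumed) puts about 16% of women above 100%. Capping at 100% gives about +2.3, +3.9 and +6.9 for both minus neither, and -0.8, -1.3 and -2.0 within met-both.

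**5. Stratum size.** Under these rates met-both holds about 4 to 6 of 86 usual-care women. Even with four equal strata (about 21 per arm in each), power for a 5-point difference within a stratum is about 35%.

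**The case against.** The strongest reply is that the analysis is expressly exploratory, sits beside an intention-to-treat plan covering every hypothesis, and drives no sample size or decision. That stands and limits the weight of the point. It does not make diet versus exercise estimable, and the paragraph carries no caveat that the comparison is non-randomized.

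Several stronger readings are tempting but go beyond the documents.

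- A reader might infer that the strata are fixed at 1 or 2 years. No visit is named. Adherence is also assessed at baseline, both questionnaires are scheduled post-chemotherapy, and attendance, log book and Fitbit data accrue during chemotherapy. The supportable statement is that the visit is unspecified and that every follow-up questionnaire is too late for RDI. The post-chemotherapy visit does not rescue the analysis: it also follows RDI, the activity recall is the past week, and no recall window is given for the food questionnaire.
- A reader might infer that eligibility rules out meeting either guideline at baseline. The diet screen is fewer than 7 fruit and vegetable servings a day, whereas Table 3 sets 5 or more and dietary adherence is judged by the Healthy Eating Index. A woman eating 5 or 6 servings is eligible and meets that Table 3 item.
- A reader might take the illustration as the size of the time-order bias, or of the diet-versus-exercise bias. It is neither. A common cause has no time order, and the same confounding would appear with exposure measured during chemotherapy.
- The time-order objection applies to RDI and dose adjustment. It is much weaker for endpoints measured after the adherence visit, such as endocrine adherence at 2 and 5 years. The absence of a randomized contrast applies to all endpoints.

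**Conclusion.** The point holds in this form. With one combined arm and strata defined after randomization, the planned analysis cannot show the separate roles of diet and exercise, and its arm comparisons within strata are not protected by randomization. That conclusion rests on the design alone. For RDI and dose adjustment there is the further problem that all scheduled follow-up questionnaires come after the outcome is complete.

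The size is not known. A modest link between tolerance and adherence would be enough to produce differences between strata comparable with the 5-point design target, but this depends on assumed adherence rates and an assumed correlation for which the documents give no value. The primary and secondary intention-to-treat results are untouched. The analysis should be changed before it is run, but it does not threaten the trial's main conclusions.

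**What to change.** 1. In item 12, remove the sentence claiming that this analysis informs the role of diet versus exercise.
2. Do not estimate arm effects within strata of post-randomization adherence.
3. For RDI and dose adjustment, report only a descriptive association within the intervention arm, using session attendance, log book and Fitbit data recorded before the last infusion. State that tolerance may confound it. Express attendance as a share of sessions scheduled: if counselling starts with chemotherapy, the schedule gives about 3 + 2 x 2 = 7 sessions in three months and 3 + 2 x 4 = 11 in five, so a raw count would follow the regimen. If the post-chemotherapy questionnaires are used, label them as measured after RDI.
4. For outcomes measured after an adherence visit, name the visit and label the result an observational association.

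This is a change of wording with no new data collection. The cost is giving up an exploratory diet-versus-exercise claim that the design cannot support.
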